#### **9.4.4. Post-void Residual Urine Volume**

PVR urine volume is assessed by ultrasound or bladder scan after the participant has performed a voluntary void. If a participant is required to begin use of CIC post treatment, the PVR urine volume will be measured after the participant has attempted to void voluntarily and prior to a catheterization. If a participant is not able to spontaneously void despite trying, then this will be recorded on the CRF and the PVR will not be measured.

After randomization, should a PVR urine volume indicate a clinically meaningful elevation, the participant should be asked to void once again (allowing the participant sufficient time to void). The PVR urine volume will then be re-assessed. For participants who have a PVR urine volume measurement repeated, only the repeat value should be recorded in the eCRF. Guidance on how to manage an elevated PVR, observed at any routine study visit or additional follow-up visit is provided. In summary, posttreatment PVR urine volume is divided into 3 categories:

- i) < 200 mL
- ii) between  $\geq 200$  mL and < 350 mL
- iii)  $\geq 350$  mL

Protocol required action depends on the PVR category as does the need for further visits to evaluate the participant. The need for CIC is also dependent on the PVR as well as the participant symptoms. This guidance is to ensure participants are appropriately followed up and CIC is only initiated when required (while also ensuring any unnecessary intervention is limited). Further details are given below.

This guidance does not preclude further actions if the investigator deems it necessary.

- i) PVR < 200 mL

No protocol required action needs to be taken. Participant continues to be followed as per the schedule of visits and procedures.

- ii) PVR  $\geq 200$  mL and < 350 mL

If a PVR of  $\geq 200$  mL but < 350 mL is identified at any posttreatment visit, the investigator will assess the participant for any spontaneously reported associated symptoms (such as voiding difficulties or sensation of bladder fullness), with the resulting action to be as follows:

**BOTOX® (Botulinum Toxin Type A)  
Purified Neurotoxin Complex**

a) If a participant reports associated symptoms that in the opinion of the investigator requires CIC to be initiated, then CIC should be managed as detailed in the CIC section (Section 9.4.5).

b) If a participant does not report any symptoms or if they report associated symptoms that, in the opinion of the investigator, do not require CIC then the following will occur:

- The participant will be seen for an additional follow-up visit 1 week later, at which time the PVR and any associated symptoms will be reassessed and central laboratory urine analysis and culture/sensitivity will be performed. At this reassessment visit:
  - if the PVR is increasing and is associated with symptoms, that in the investigator's opinion require CIC, then CIC should be initiated and managed as detailed below in the CIC section
  - if the PVR is  $\geq 350$  mL then CIC should be initiated and managed as detailed below in the CIC section
  - if the PVR is increasing but is not associated with symptoms or is associated with symptoms that in the opinion of the investigator do not require CIC, then the participant will be seen 1 week later to determine if CIC has become warranted and should be initiated based on PVR and/or any associated symptoms. At this additional reassessment visit:
    - a central laboratory urine analysis and culture/sensitivity will be collected
    - if in the investigator's judgment CIC should be initiated, then CIC should be managed as detailed below in the CIC section
    - if CIC is not initiated and PVR continues to increase, the investigator will determine whether additional follow-up visits should occur
  - If the PVR is decreasing or is unchanged then the participant will continue per the protocol schedule of visits and procedures.

iii)  $\text{PVR} \geq 350$  mL

If a PVR of  $\geq 350$  mL is identified at any posttreatment visit (regardless of symptoms) then CIC will be initiated as detailed in the CIC section.

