#### **9.2.6. Study-Specific Definitions for Particular Adverse Events**

##### Definition of Adverse Event of Urinary Retention

An adverse event of urinary retention should only be recorded when a participant has an elevated PVR that requires intervention with CIC according to the following criteria:

- Participant has a PVR of  $\geq 350$  mL (regardless of symptoms), OR
- Participant has a PVR  $\geq 200$  mL and  $< 350$  mL and the participant reports associated symptoms ie, voiding difficulties, sensation of bladder fullness that in the investigator's opinion require CIC.

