##### Definition of Adverse Event of Residual Urine Volume

An adverse event of residual urine volume should be recorded if, in the investigator's opinion, the raised PVR is clinically significant but does not fulfill the above definition for urinary retention.

The investigator should use the information from the regular assessment of PVR urine volume and the need to catheterize for elevated PVR to assess the stop date of the adverse events.

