#### **9.4.5. Clean Intermittent Catheterization**

The following guidance should be used for the initiation of CIC in this study. Sterile, single use intermittent catheters should be used. Indwelling catheters should not be used in this study.

**BOTOX® (Botulinum Toxin Type A)  
Purified Neurotoxin Complex***Initiation of Clean Intermittent Catheterization*

As described above in the [PVR section](#), CIC should be initiated per protocol when one of the following criteria is fulfilled:

- PVR is  $\geq 350$  mL at any posttreatment visit, regardless of whether the participant reports associated symptoms
- PVR is  $\geq 200$  mL and  $< 350$  mL and the participant spontaneously reports associated symptoms (ie, voiding difficulties, sensation of bladder fullness) that in the opinion of the investigator requires CIC.

The following will occur when initiating CIC (for elevated PVR as described above):

1. CIC is implemented and the participant should be instructed to perform CIC using sterile, single-use catheters (which will be provided to the participant)
2. An adverse event of urinary retention is recorded
3. Central laboratory urine analysis and culture/sensitivity are performed as per routine requirements at each study visit
4. The participant will be seen for a follow-up visit 1 week later where the PVR, associated symptoms, central laboratory urine analysis and culture/sensitivity will be reassessed. The investigator will determine whether the participant can then be followed per protocol scheduled study visits or whether additional follow-up visits should occur.

Once CIC is initiated, the status of CIC use should be documented in the participant record at each visit (ie, use/nonuse).

*Cessation of Clean Intermittent Catheterization*

CIC should be discontinued when the following criteria are fulfilled:

- the participant does not have any associated symptoms which in the opinion of the investigator require CIC AND
- the PVR is  $< 350$  mL

The date of discontinuation of CIC should be documented. If the investigator deems that CIC should not be discontinued even though the above criteria are fulfilled, then this should be documented and the reason given. Upon discontinuing CIC the participant will be seen for a follow-up visit 1 week later where the PVR, associated symptoms, central laboratory urine

**BOTOX® (Botulinum Toxin Type A)  
Purified Neurotoxin Complex**

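### The by-visit PVR tables drop the reading that triggered a recheck and have no place for a participant who cannot void

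*Protocol*

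**What the plan says.** **Protocol 9.4.4** has PVR measured by ultrasound or bladder scan after a voluntary void. For a participant who has had to begin CIC, it is measured after an attempt to void and before catheterizing. The next sentence covers a participant who cannot void despite trying: "then this will be recorded on the CRF and the PVR will not be measured". It does not say whether it is limited to CIC users. For a PVR of 200 to <350 mL where CIC is not started, "The participant will be seen for an additional follow-up visit 1 week later", with PVR reassessed. If PVR has risen but CIC is still not started, a second reassessment follows a week after that.

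**Protocol 9.4.5** says "CIC should be initiated per protocol when one of the following criteria is fulfilled", and both criteria that follow are PVR ranges. After CIC starts, "The participant will be seen for a follow-up visit 1 week later where the PVR, associated symptoms" and urine tests are reassessed. On stopping, "CIC should be discontinued when the following criteria are fulfilled"; these are no symptoms requiring CIC and a PVR below 350 mL.

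**Protocol 9.2.6** says "An adverse event of urinary retention should only be recorded when a participant has an elevated PVR that requires intervention with CIC". A residual urine volume event is recorded if, in the investigator's opinion, "the raised PVR is clinically significant but does not fulfill the above definition for urinary retention". The investigator uses "the regular assessment of PVR urine volume and the need to catheterize for elevated PVR to assess the stop date" of these events.

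**SAP 11.4.2 (Stage 1 and Stage 2)** gives PVR descriptive statistics by visit and at end of study. It also gives counts in four categories (<100, 100 to <200, 200 to <350 and ≥350 mL) by postbaseline visit and for the study as a whole. Neither SAP has a category for inability to void or says which reading sets the whole-study category.

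**SAP 15.1 (both stages)** applies its windows to efficacy and safety analyses. Where a window holds two or more visits, the latest one with a value is used. All readings are kept for listings and for flagging potentially clinically significant (PCS) values, but PVR is not in either PCS table. **SAP 15.4** makes the last postbaseline value the end-of-study value when unscheduled visits occur.

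**The concern.** The protocol schedules an extra PVR because a reading was high enough to need action. The SAP rule then prefers the extra reading to the one that caused it. Read together, the two rules remove the action-triggering PVR from the by-visit table whenever both fall in one window. The visit means and changes from baseline use the same selected value.

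The no-void case is a second gap in the same table. A participant who cannot void has a CRF entry but no volume, and the four categories give that entry nowhere to go.

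Urinary retention is one of the two adverse events of particular interest in the sample size sections. The PVR tables are where a reader would look for how far emptying was impaired at each dose and visit, so they should show the readings that called for follow-up.

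**Working it through.** **1. The plan's own retention figures.** Protocol 10.1 and Stage 1 SAP section 13 give the chance of at least one retention event at rates of 6% to 7%. With 8 BOTOX participants: 1 − 0.94^8 = 0.39 and 1 − 0.93^8 = 0.44. With 16: 1 − 0.94^16 = 0.63 and 1 − 0.93^16 = 0.69. All match the plan. They concern adverse event counts, which window selection does not alter, so nothing below changes them.

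**2. Does the required recheck fall in the same window as its trigger?** Target days and windows come from Table 15.1-1 of each SAP; the one-week interval comes from Protocol 9.4.4 and 9.4.5. First recheck = target + 7. Second recheck, where required, = target + 14. The latest trigger day whose first recheck stays inside = window end − 7.

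| Visit | Target | Window | +7 | +14 | Latest trigger day |
|---|---|---|---|---|---|
| Week 2, both stages | 15 | 2–29 | 22 | 29 | 29 − 7 = 22 |
| Week 6, both stages | 43 | 30–64 | 50 | 57 | 64 − 7 = 57 |
| Week 12, Stage 2 | 85 | 65–99 | 92 | 99 | 99 − 7 = 92 |
| Week 16, Stage 2* | 113 | 100–127 | 120 | 127 | 127 − 7 = 120 |
| Week 20, Stage 2* | 141 | 128–155 | 148 | 155 | 155 − 7 = 148 |

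*Assumes that PVR is measured at this visit; the schedule of activities is not visible.

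Every first recheck from an on-target visit lies in its trigger's window, and so does every second one. The trigger visit can be late by 22 − 15 = 7 days at Week 2, 57 − 43 = 14 days at Week 6 and 92 − 85 = 7 days at Stage 2 Week 12 before this stops being true. In Stage 1 the Week 12 window is open-ended from Day 65, but Week 12 is the exit visit, so a later recheck may not occur.

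**3. Which value reaches the table?** Under 15.1, the recheck. If PVR has fallen below 200 mL, the table shows no raised reading for that visit. If PVR has risen, the table shows the higher value, unless a further visit follows in the window. For example, a PVR of 200 to <350 mL on Day 15 and ≥350 mL on Day 22 leads to CIC and a revisit on Day 29. Day 29 is still in the Week 2 window, so both earlier readings drop out if a PVR is obtained that day. The replacement can thus be lower or higher than the trigger.

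**4. The participant who cannot void.** There is no PVR at that visit. If another PVR falls in the window, it stands in; otherwise the participant is absent from that visit's table. No recheck is required after a no-void entry alone, so a stand-in arises only if CIC has started or another visit happens to fall in the window.

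**The case against.** Four points deserve weight.

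*Section 15.4, not 15.1, might govern unscheduled safety readings.* It is headed for repeated and unscheduled assessments, but apart from baseline it assigns a value only for end of study and is silent on by-visit tables. Section 15.1 covers safety analyses and refers to two or more visits without restriction, so replacement follows from the rules as written. What stands is that the table specifications are in a separate document, not seen here, which may limit by-visit tables to scheduled visits, define the whole-study category or add a row.

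*Taking the latest value in a window is a prespecified and ordinary convention.* True, and no directional bias is shown. The difficulty is specific to PVR, where the extra visit is caused by the reading that it replaces.

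*The information is not lost.* All assessments are listed, inability to void is entered on the CRF, and both SAPs summarize catheterization by reason. This stands and limits the effect to the tables.

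*The no-void sentence may concern only participants already on CIC.* It directly follows the sentence about them, so this is a natural reading. Retention has then already been recorded, and the CIC-stop criterion is simply not met while no PVR can be taken. A reader might infer that retention events will be missed. That needs the broad reading, on which a participant not on CIC who cannot void meets none of the PVR-based criteria. The text does not settle the scope, and even then the investigator keeps discretion to act and must still record adverse events. What remains is a question of how the event is classed.

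**Conclusion.** The point holds for the descriptive PVR tables in both SAPs. As written, a required one-week recheck after an on-target visit replaces the triggering PVR at Week 2 and Week 6 in both stages and at Week 12 in Stage 2. A participant who cannot void has no category. The number of participants affected cannot be computed: the documents give no rate of PVR ≥200 mL and no rate of inability to void. The result rests on visits near target and on the unseen table specifications not already overriding 15.1.

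Two stronger conclusions are tempting and not supported. One is that the retention adverse event count is biased: window selection does not touch it, and the no-void sentence would affect it only on the broad reading. The other is that dose escalation or Stage 2 dose selection is distorted: the data review committee reviews unblinded safety data, and nothing visible says that it relies on the 11.4.2 by-visit tables.

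**What to change.** In section 11.4.2 of both SAPs:

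- Assign the by-visit category from the highest recorded PVR in the window, unscheduled rechecks included, and the whole-study category from the highest recorded postbaseline PVR. Using the scheduled-visit value instead would not be equivalent, because it would hide a PVR that worsens at the recheck, a path that Protocol 9.4.4 foresees. If the visit means stay on the 15.1 rule, a footnote should say so.
- Add an unable-to-void category taken from the CRF entry. Keep these participants in the denominator, and do not let a numeric PVR in the same window overwrite the entry.

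The cost is one table row and a sentence or two in each SAP, with no new procedure. The no-void entry must be codable from the CRF, which cannot be checked here. The tables may look slightly less favourable, and the new row may often be zero.

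Separately, as a minor clarification, the sponsor should reconcile Protocol 9.2.6, 9.4.4 and 9.4.5. They should state whether the no-void sentence applies only to participants already on CIC, and how a participant with no PVR is classed under the adverse event definitions and the CIC start and stop criteria. No clinical rule is proposed here.

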#### **9.4.5. Clean Intermittent Catheterization**

The following guidance should be used for the initiation of CIC in this study. Sterile, single use intermittent catheters should be used. Indwelling catheters should not be used in this study.

**BOTOX® (Botulinum Toxin Type A)  
Purified Neurotoxin Complex***Initiation of Clean Intermittent Catheterization*

As described above in the [PVR section](#), CIC should be initiated per protocol when one of the following criteria is fulfilled:

- PVR is  $\geq 350$  mL at any posttreatment visit, regardless of whether the participant reports associated symptoms
- PVR is  $\geq 200$  mL and  $< 350$  mL and the participant spontaneously reports associated symptoms (ie, voiding difficulties, sensation of bladder fullness) that in the opinion of the investigator requires CIC.

The following will occur when initiating CIC (for elevated PVR as described above):

1. CIC is implemented and the participant should be instructed to perform CIC using sterile, single-use catheters (which will be provided to the participant)
2. An adverse event of urinary retention is recorded
3. Central laboratory urine analysis and culture/sensitivity are performed as per routine requirements at each study visit
4. The participant will be seen for a follow-up visit 1 week later where the PVR, associated symptoms, central laboratory urine analysis and culture/sensitivity will be reassessed. The investigator will determine whether the participant can then be followed per protocol scheduled study visits or whether additional follow-up visits should occur.

Once CIC is initiated, the status of CIC use should be documented in the participant record at each visit (ie, use/nonuse).

*Cessation of Clean Intermittent Catheterization*

CIC should be discontinued when the following criteria are fulfilled:

- the participant does not have any associated symptoms which in the opinion of the investigator require CIC AND
- the PVR is  $< 350$  mL

The date of discontinuation of CIC should be documented. If the investigator deems that CIC should not be discontinued even though the above criteria are fulfilled, then this should be documented and the reason given. Upon discontinuing CIC the participant will be seen for a follow-up visit 1 week later where the PVR, associated symptoms, central laboratory urine

**BOTOX® (Botulinum Toxin Type A)  
Purified Neurotoxin Complex**

analysis and culture/sensitivity will be reassessed. The investigator will determine whether the participant can then be followed at regularly scheduled study visits or whether additional follow-up visits should occur based on PVR and/or associated symptoms.

**9.4.6. Bladder and Kidney Ultrasound**

Abdominal ultrasound of the bladder and kidneys will be performed with the bladder at least half full. Participants are excluded from this study if the screening ultrasound demonstrates the presence of bladder stones and/or intra-luminal filling defects of the bladder suggestive of malignancy. In the case of unclear new findings identified at the exit visit ultrasound which may be suggestive of stones (kidney, ureter, or bladder), other diagnostic measures must be performed in order to confirm the presence of stones, rule out bladder malignancy (eg, x-ray with or without contrast, urogram, CT scan, MRI or cystoscopy and histopathological confirmation).

**9.4.7. Concomitant Medications and Concurrent Procedures**

Concurrent procedures and concomitant medication (including name of medication, dose, route, and date) information will be collected at each study clinic and phone visit starting at the time of screening and ending at the participant Exit Visit. All concomitant medications and concurrent procedures must be recorded in the eCRF with all specific details associated with each use of the medication/procedure.

**9.5. Pharmacokinetics**

Pharmacokinetic parameters are not evaluated in this study.

**9.6. Pharmacodynamics**

Pharmacodynamic parameters are not evaluated in this study.

**9.7. Genetics**

Genetics are not evaluated in this study.

**9.8. Biomarkers**

Biomarkers are not evaluated in this study.

**BOTOX® (Botulinum Toxin Type A)**  
Purified Neurotoxin Complex

## 10. Statistical Considerations

### 10.1. Sample Size Determination

For Stage 1, approximately 50 to 70 participants will be enrolled to ensure that 10 to 20 individuals are randomized into each of the 4 cohorts (100 U Cohort: n = 10; 300 U Cohort: n = 20; 400 U Cohort: n = 20; 500 U Cohort: n = 20) to provide sufficient data in the analysis and interpretation of safety results. Two particular adverse events of interest are urinary retention and UTI. From previous BOTOX studies, the percentage of participant in the BOTOX-treated population experiencing these adverse events is 6% to 7% for urinary retention and 20% to 30% for UTI. In cohort 1, the probability of observing at least one BOTOX-treated participant experiencing these adverse events is 0.39 to 0.44 and 0.83 to 0.94, respectively. For the other cohorts, the probability of observing at least one BOTOX-treated participant experiencing these adverse events is 0.63 to 0.69 and 0.97 to ~ 1, respectively.

For Stage 2, 50 participants are required for each of the 4 BOTOX treatment groups and 50 participants are required for the placebo group in order to obtain approximately 72% power to detect a between group difference of 1.8 episodes in change from baseline to Week 12 in the number of episodes of urinary incontinence per day between the BOTOX and placebo treatment groups. Sample size calculations are based on a two-sample t-test assuming a common standard deviation (SD) of 3.5 episodes and a 2-sided type I error rate of 0.05. In order to account for participant attrition (estimated to be 5%), the sample size was increased to 53 participants for each treatment group, amounting to a total of 265 randomized participants required for Stage 2. Additionally, using these samples sizes, the probability of observing at least one occurrence of urinary retention or UTI in the BOTOX-treated population in Stage 2 is nearly 1.

**Table 10-1** **Sample Size Assumptions for Stage 2**

Parameter	Assumption/Estimate
Primary endpoint	Change from baseline to Week 12 in the number of episodes of urinary incontinence per day between BOTOX and placebo treatment groups
Mean/risk difference a	1.8 episodes
SD a	3.5 episodes
$\alpha$	0.05
Sides	2
Power	72%
N per group	50
Attrition rate	5% at Week 12
N total	265
N per group estimated	53

a Based on previous BOTOX studies and relevant details

Overall, a total of 315 to 335 randomized participants are required for the entire study.

